9. STUDY DEVELOPMENT

9.1. Coverage of Clinical Trial Unit

Clinical bioequivalence trials are conducted in the Phase I room. This one has twelve chairs, one for each subject. It is possible to realize groups of twelve people until reaching the totality of the subjects recruited.

It consists of three consultations, two carts where the most frequently used material is stored by the nurses and in the most accessible way, as well as a stop cart. It is strategically located, in front of the Resuscitation Unit in case emergency assistance is necessary. It consists of four electrocardiographs, three portable tensiometers and one fixed one. Four tympanic thermometers, two aneroid sphygmomanometers, two phonendoscopes, a stadiometer and a scale. Two toilets for use by volunteers with bell, in case of assistance, as well as security cameras and a room of common use for the personnel involved.

9.2. Workflow of Clinical Trials Unit for bioequivalence studies

In any of the bioequivalence trials, subjects are recruited who meet the inclusion and exclusion criteria added to those described above.

It supposes an income around 24 h, according to the design of each trial, and the intravenous cannulation to each subject to perform the pharmacokinetics of each drug. A recruiting visit is made to inform about the clinical trial in question, the Patient Information Sheet and the Informed Consent are delivered.

It is ensured that they do not carry any disease; the following is done:

- Blood and urine extraction. Biochemistry, Hematology, Serology and urinary sedimentation. - Vital signs. Blood Pressure (BP), Heart Rate (HR), Temperature (T).
- Anthropometry Weight, Size, Body Mass Index (BMI)
- Electrocardiogram (ECG).
- Physical exam. Concomitant treatment.

In this visit will be carried out, only the selection of subjects according to the criteria of inclusion / exclusion of the trial that takes place in the unit. Subjects enter the night before the prescribed day to perform pharmacokinetics. Next day, at 08:00 h, intravenous cannulation is started by the nursing team. The subjects remain fasting from dinner on the day of admission. The medication is always administered after the canalization and once a basal blood sample has been extracted in tubes whose additive is dipotassium ethylenediaminetetraacetic acid (K₂EDTA).

9.3. Workflow between Clinical Trial Unit and ECYPVEN-H/17

It is the day of the pharmacokinetics or, day two of entrance of the essay of bioequivalencia, when it will carry out the application of the three interventions and the comparator.

9.4. Development of fieldwork of the trial

The first evaluation of the VIA scale (36) will be carried out, according to the number of optimal puncture points (PPO), before the application of the arm assigned by the main researcher and will correspond to the inclusion and exclusion criteria; pre-intervention assessment. This will be transcribed as the first VIA scale assessment (36).

In the interventions, the VIA scale will be evaluated twice (36). The second assessment will be carried out after the application of the intervention or randomly assigned comparator; and before performing venipuncture.

In the case of the comparator, it will only be evaluated once; It will not be assessed if it denotes a change of stage, since no intervention is applied. If this corresponds to the first period, the registration stage of the inclusion / exclusion criteria will be transcribed, if it corresponds to the second period, the corresponding nurse will assess it.

In both cases, the intervention or comparator will be applied, the success or failure in successful venipuncture will be recorded on the first attempt. In the case of failure, the attempt number to which the catheterization was possible will be recorded. Table 2

| ORGANIZATION CHART ACCORDING TO VISITS | | |
|---|-----------------|---|
| ENROLLMENT VISIT | FIRST DAY ENTRY | SECOND DAY ENTRY |
| 
 1. Information Sheet 2. Informed consent form. 3. Training for the nurses listed on the form. | X | 
 1. Subjects inclusión according to inclusión and exclusión criteria VIA assessment 2. Randomized assignment 3. Intervention/comparator assigned application. 4. Post intervention VIA assessment. 5. VAS pain assessment. 6. FITZPATRICK scale skin assessment 7. Hemolysis analysis. |

Table 2. Organization chart according to visits. Own elaboration.

This organization chart, Table 2, will be specific to the first period of the clinical trial. Another detailed organization chart has been prepared for the two study periods in section 9.7.3.

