5.2.2. Secondary objectives

- o Identify the effectiveness of all the methods used in antebrachial venipuncture, in what refers to venipuncture at the first attempt.
- o Design and validate a visual scale of hemolysis.
- o Evaluate the intensity of hemolysis of blood samples, in what refers to the method applied, respectively.
- o Identify the frequency of successful venipuncture at the first attempt, and analyze whether there is an association between it and the demographic characteristics of the individuals.
- o Analyze the correlation between methods used, intensity of hemolysis and pain.
- o Identify and quantify adverse events, as well as their relationship with skin types.

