9.7. CLINICAL FINDINGS AND MATERIAL RESOURCES INVOLVED

9.7.1. Pain assessment

The evaluation of the pain will be carried out through the scale validated Visual Analog Scale (VAS) / numerical (45). Linear scale from zero to ten, from minimum pain to maximum perceived pain, escalating with integers in increasing order. The use of this scale is considered pertinent because it has been validated for the detection of both chronic and acute pain; through changes in temperature and for groups of individuals (45,46).

The individual will be provided with this scale, in paper format, so that he self-expresses the pain perceived in the venous cannulation with the randomly assigned method. It is provided immediately after the fixation of the vein catheter.

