9.7.2. Evaluation of skin types

An evaluation of the skin type will be carried out according to Fitzpatrick's validated scale. Scale commonly used in the field of dermatology, which consists of six skin types according to their visual characteristics and the frequency of burning before sun exposure (47). The phototype one refers to white skin that always burns with sunlight and, phototype six refers to dark skin that never burns. The identification of these phototypes is self-expressed by the subject, valuing the medial anatomical region of the arm; part considered by experts as less exposed to sunlight (47,48).

The concordance of the self-expressed skin type according to this scale and the melanin concentration with spectrophotometry have been evaluated. Some studies agree on the finding of concordances in some phototypes and in others, but they point out that it could be due to the self-evaluation of the subject; even so all of them consider that it is a good estimator of the skin type. However, other studies have validated the scale for all phototypes only in women (49), and another study has validated five of the six phototypes, with the exception of the first one, due to the characteristics of their mixed accessible sample (50). All the findings consider appropriate the scale to assess the type of skin according to the color and frequency of tanning / burning, and not so to identify the genetic disposition. Therefore, it could be considered appropriate to use the Fitzpatrick scale to identify the type of skin and the frequency of possible erythemas caused by topical heat in this study (47).

Individuals will be provided with said scale, in paper format, and they will themselves indicate the item in which they are identified. They will be reminded to look at the medial region of the arm.

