The design and validation of the scale are collected, in detail, in section 14.2.3.

| ORGANIZATION CHART OF CLINICAL FINDING ACCORDING TO VISITS | | |
|--|-----------------|---|
| FIRST PERIOD | WASH-OUT PERIOD | SECOND PERIOD |
| VAS/NUMERIC scale for pain assessment FITZPATRICK scale for skin assessment Hemolysis analysis 
 ▪ Baseline blood sample ▪ Afternoon blood sample ▪ Evening blood sample | X | VAS/NUMERIC scale for pain assessment Hemolysis analysis 
 ▪ Baseline blood sample ▪ Afternoon blood sample ▪ Evening blood sample |

Table 3. Organization chart of clinical findings according to visits. Own elaboration.

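### Self-rated Fitzpatrick skin type is scheduled after the period-1 method is applied, so 20 of the 40 heat-exposed subjects rate it after heat and 20 before

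*Combined protocol and SAP*

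**What the plan says.** Section 9.4, Table 2, numbers the steps of the second day of admission. Eligibility with the first VIA assessment and randomisation come first, then "3. Intervention/comparator assigned application", then "4. Post intervention VIA assessment. 5. VAS pain assessment. 6. FITZPATRICK scale skin assessment". The text below the table adds: "This organization chart, Table 2, will be specific to the first period of the clinical trial".

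Table 3 (section 9.7.3) lists, in its first-period column, "VAS/NUMERIC scale for pain assessment FITZPATRICK scale for skin assessment Hemolysis analysis". Its second-period column repeats pain and hemolysis but has no skin-type entry, so there is one rating per subject.

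Section 9.7.1 fixes the time of the pain scale, the step just before the skin-type form: "It is provided immediately after the fixation of the vein catheter".

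Section 9.7.2 makes the rating a self-report: "Individuals will be provided with said scale, in paper format, and they will themselves indicate the item in which they are identified". The scale rests on skin appearance and on how often the skin burns in the sun, and subjects are reminded to look at the medial part of the arm. The stated purpose is "to identify the type of skin and the frequency of possible erythemas caused by topical heat in this study".

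The objective served is in section 5.2.2: "Identify and quantify adverse events, as well as their relationship with skin types". Section 14.3 assigns a Kruskal-Wallis test to it.

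**The concern.** Skin type is a stable trait and is meant to explain who develops erythema. It should therefore be recorded before the exposure that can cause the erythema. Here the randomised sequence decides whether it is recorded before or after. Subjects allocated to heat or the combination in period 1 fill in the form after the sacks have been applied. Those allocated to the comparator first fill it in before any heat, about a week earlier (washout, section 6.5).

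The form is open to influence, because it is self-rated and partly about how readily the skin burns. Subjects also know which method they received (section 6.4). Someone who has just seen their skin redden may choose a more burn-prone type, from what they still see or from what they remember. That would create or inflate the association that the objective looks for. The bias would also point the way the protocol already expects, since section 9.8 reports that earlier heat erythema was registered only in subjects with sensitive skin.

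**Working it through.** **1. Is the order chronological?** Section 9.4 places the second VIA assessment after application and before venipuncture. Section 9.7.1 places the pain scale after catheter fixation. Steps 3, 4 and 5 of Table 2 are therefore in time order, and the skin-type form is step 6. Table 3 also lists it after the pain scale. No section places it at enrolment or before application.

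**2. How many subjects are affected?** Section 6.3 gives, in each block of 12 envelopes:

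| Sequence | Envelopes | Skin type rated |
|---|---|---|
| Heat, then comparator | 2 | after heat |
| Comparator, then heat | 2 | before heat |
| Combination, then comparator | 2 | after heat |
| Comparator, then combination | 2 | before heat |
| Pressure, either order | 4 | no heat |

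- Total: 12 × 5 = 60, which reproduces the plan's figure.
- Heat-exposed: (2 + 2 + 2 + 2) × 5 = 40.
- Rated after heat: (2 + 2) × 5 = 20, and 20/40 = 50%.
- With 54 completers and balance kept: 18/36 = 50%.
- If all 6 losses were heat-exposed subjects from one order, the share would lie between 14/34 = 41% and 20/34 = 59%.

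**3. How large could the distortion be?** The documents give neither the erythema rate nor the chance that reddening changes a self-rating, so this step is a sensitivity range built on assumptions:

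- 40 heat-exposed subjects, 20 of them rated after heat;
- phototypes I to VI distributed 5/20/40/25/7/3%;
- no true association between skin type and erythema;
- each heat-first subject with erythema moves one type towards burn-prone with a given shift probability;
- Kruskal-Wallis test at 5%, several thousand simulated trials per setting.

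| Shift probability | False-positive rate, erythema in 20 to 40% |
|---|---|
| 0 | about 5% |
| 0.1 to 0.25 | about 5 to 6% |
| 0.5 | about 9 to 10% |
| 1 | about 20 to 27% |

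With 36 subjects (54 completers, balanced), the last two rows become about 8 to 10% and 18 to 23%. With erythema in only 10% of 40 subjects, they become about 7.5 to 8% and 12 to 13%.

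**4. What else uses skin type?** It is listed as a secondary variable in section 14.1.1, and section 14.1.3.1.2 admits the secondary variables as explanatory terms in the logistic regression. The McNemar test, the sample size and the hemolysis scale work do not use it.

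**The case against.** The case against a material bias is strong in several respects.

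- **Site.** Subjects are told to look at the medial arm (section 9.7.2), whereas the sacks lie on the area to be punctured, usually the forearm from the wrist upwards (section 8.1.1). The documents do not say that the inspected skin is the heated skin, or even that it is on the same arm.
- **Time.** Section 9.8 says erythema resolves within minutes. The tourniquet or cuff, the second VIA assessment, venipuncture, catheter fixation and the pain scale all come before the form.
- **Nature of the scale.** It rests partly on lifelong response to sun. The remark in section 9.7.2 about self-evaluation concerns agreement with measured melanin, and is not evidence that heat erythema moves the answer.
- **Reach.** One non-main secondary analysis is affected. Half of the heat-exposed subjects rate before heat, so a comparison by sequence could give some indication of bias.
- **Numbering.** The enrolment column of Table 2 lists nurse training after consent, so the table's numbers are not strictly a per-subject sequence.

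The first four points stand as limits on size. The last has little force, because the day-2 steps agree with the text of sections 9.4 and 9.7.1.

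A reader might infer that these 20 subjects rate their skin while looking at visible erythema, or that the test will give false positives in a fifth to a quarter of trials. The documents support neither. Redness may have faded or lie elsewhere, and the highest figures require every reddened heat-first subject to shift by a full type. What remains is possible influence from visible or recalled redness, and nothing in the plan excludes it.

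**Conclusion.** The point holds as a minor design flaw. The timing and the count follow directly from Tables 2 and 3 and the envelope scheme: 20 of 40 heat-exposed subjects record the explanatory variable after the outcome and 20 before it. The resulting bias in the skin-type and adverse-event analysis is plausible, but its size is unknown. It is close to nil if self-ratings rarely shift (a probability of 0.25 or less) and moderate if half of the reddened heat-first subjects shift. It is large only in the extreme case. These sizes rest on the assumed erythema rate, phototype distribution and one-type shift, none of which the documents give. The primary McNemar test is untouched. It is worth correcting because it costs nothing now and cannot be repaired once the forms have been filled in.

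**What to change.** In Table 2, move the Fitzpatrick form to the enrolment visit, or to day 2 before randomisation, beside the eligibility VIA assessment. Align Table 3 with this, and state in section 9.7.2 that the form is completed before any method is applied. Heat-exposed subjects who rate after heat then fall from 20 of 40 to 0 of 40.

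The cost is a line in each of those places. The same paper form is used, with no extra visit and no change to the sample size or the procedures.

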9.5. Quality control and monitoring

The present work does not work with a monitor since the promoter and main researcher coincide in the same person. In addition, when considering a low-level intervention study, the following is established:

The concept of "low-level intervention clinical trial", which calls for adopting less rigorous standards in aspects such as monitoring, the content of the master file or traceability, without impairing the safety of the individuals participating in them (2).

However, the principal investigator of this trial and the principal investigator of the bioequivalence clinical trial and collaborating researcher of this one, will be in charge of monitoring the course of the clinical trial according to what is established in the protocol. Likewise, they are responsible for the good progress of the study, for carrying out quality controls and the degree of cooperation of different collaborators not mentioned in this document.

9.6. Thermoregulation monitoring

The temperature and humidity will be monitored with an environmental clock, oh! Haus & co.°, with CE marking. It will collect the temperature of the whole phase I; between 23 and 25 °C with a humidity of 27 and 31% approximately. Likewise, light will always be artificial.

The clothing of the subjects is harmonized by a hospital cotton pajama. Therefore the thermoregulation is considered to be roughly harmonized and that the intersubject variability in that aspect is not high.

9.7. CLINICAL FINDINGS AND MATERIAL RESOURCES INVOLVED

9.7.1. Pain assessment

The evaluation of the pain will be carried out through the scale validated Visual Analog Scale (VAS) / numerical (45). Linear scale from zero to ten, from minimum pain to maximum perceived pain, escalating with integers in increasing order. The use of this scale is considered pertinent because it has been validated for the detection of both chronic and acute pain; through changes in temperature and for groups of individuals (45,46).

The individual will be provided with this scale, in paper format, so that he self-expresses the pain perceived in the venous cannulation with the randomly assigned method. It is provided immediately after the fixation of the vein catheter.

9.7.2. Evaluation of skin types

An evaluation of the skin type will be carried out according to Fitzpatrick's validated scale. Scale commonly used in the field of dermatology, which consists of six skin types according to their visual characteristics and the frequency of burning before sun exposure (47). The phototype one refers to white skin that always burns with sunlight and, phototype six refers to dark skin that never burns. The identification of these phototypes is self-expressed by the subject, valuing the medial anatomical region of the arm; part considered by experts as less exposed to sunlight (47,48).

The concordance of the self-expressed skin type according to this scale and the melanin concentration with spectrophotometry have been evaluated. Some studies agree on the finding of concordances in some phototypes and in others, but they point out that it could be due to the self-evaluation of the subject; even so all of them consider that it is a good estimator of the skin type. However, other studies have validated the scale for all phototypes only in women (49), and another study has validated five of the six phototypes, with the exception of the first one, due to the characteristics of their mixed accessible sample (50). All the findings consider appropriate the scale to assess the type of skin according to the color and frequency of tanning / burning, and not so to identify the genetic disposition. Therefore, it could be considered appropriate to use the Fitzpatrick scale to identify the type of skin and the frequency of possible erythemas caused by topical heat in this study (47).

Individuals will be provided with said scale, in paper format, and they will themselves indicate the item in which they are identified. They will be reminded to look at the medial region of the arm.

9.7.3. Hemolysis evaluation

After bibliographic search, no validated methodology was found to evaluate said construct, which is why it is intended to design a scale, in spectrophotometric terms of absorbances and colorimetry; through images and / or photographs, and subsequently validate this scale throughout the fieldwork. It will be carried out in the extraction of blood samples at different times throughout the admission of healthy subjects in UECHUP.

Different cross-interferences for hemolysis have been described, which could bias the identification of their intensity, both in absorbance and in visual detection (51, 52,53) and, therefore, interfere in some analytical determinations. Cross-linked interferences such as

bilirubin and lipemia are identified, which may cause a "yellowish" color and / or "turbidity" in the plasma, respectively (53). In general it is known that lipemia acts by overestimating the intensity of hemolysis and indirectly the accuracy in the determination of blood constituents and the bilirubin denoted by an underestimation effect in the intensity of hemolysis and accuracy of the determinations of other blood constituents in concentrations, measured in milligrams / deciliter (mg / dl) (30). In addition, Saldaña IM et al has shown, in its interferogram, that there is a non-linearity relationship between the concentration of free hemoglobin in plasma and the determination of total bilirubin, denoting an underestimation of it in small concentrations of extracellular hemoglobin and subsequently producing a overestimation In the same way, it states that not only depends on the amount of hemoglobin, but also the concentration of bilirubin. (54).

Hemolysis, without cross-interference, alters the accuracy of some analytical determinations, generally increases the concentration of those determinations that occur in large concentrations at the intracellular level, and decreases those that are found at low concentrations (53). Currently, the serum indices are being used as parameters to evaluate the intensity of hemolysis. In a semiquantitative term, they defend the use of absorbance for their measurement; However, no manufacturer provides calibrators and controls for these indices, which prevents the evaluation of their analytical performance (30, 51,53).

It is denoted that at 414 nanometers (nm), where the maximum intensity of free hemoglobin in plasma is generally found, it is a specific point of measurement in which the absorbance curves of bilirubin and lipemia overlap; between 400 nm and 540 nm for the detection of jaundice whose maximum expression is evidenced at 460 nm, and between 300 nm and 700 nm for lipemia without maximum peak expression but optimal absorbance at 300 nm. Farrell CJ et al proposes a correction factor to eliminate these interferences which does not contribute. As a consequence, a possible cross-interference of hemolysis will be eliminated by monitoring the bilirubin of the subjects through blood analysis in the screening visit of the bioequivalence study. For lipemia, the analysis of those blood samples that are as remote as possible, in time, from the food intake of the volunteers; It is evident that the most common cause of lipemia is the recent intake of a meal high in saturated fats (53). Therefore it is not considered necessary to perform any correction factor for the cross-linking of bilirubin, however, if it could be useful to subject those blood samples in which lipemia is suspected to an absorbance of 650 nm, according to the schedule established for the extraction and its postparallel temporal relationship. Although at 300 nm the absorbance of lipemia is higher, it interferes with extracellular hemoglobin; not so at 650 nm (53). If there is present lipemia, in spite of its avoidance, it would be representing the

target population and the reality as it manifests an increase in blood samples without having respected a fast and these conditions are even allowed in some guidelines for the evaluation of cardiovascular risk (53); therefore, it is considered that the adjustment method could be justified to what the authors propose.

The evaluation of hemolysis will be carried out by absorbances of extracellular hemoglobin after centrifugation of these. The material resources involved and their use are the following:

1. NanoDrop™ 2000 Spectrophotometer Thermo Scientific

Device, of small size, approximately 20 cm wide, 14 cm deep and 20 cm high, equipped with a broad spectrum of Ultraviolet-Visible (190-840 nm) for micro volumes of 0.5 to 2 microliters of sample initial through fiber optics. It has the measurement of very concentrated samples without the need of previous dilutions. The quantification of the absorbance of oxyhemoglobin at 414 nm will be measured by dropping one to two microliters of the substance to be analyzed. On this substance the device emits a beam of light that crosses the sample. Depending on the beam of light traversed and, therefore, received, it is considered transmittance. Although the transmittance leads to losses due to dispersion in the solution, it is considered, according to the Lambert-Beer Law, that the transmittance and absorbances are inversely related. Absorbance is the intensity of light that the chemical component of the sample retains and, therefore, is the opposite of the received light. As a consequence, the absorbance is measured with the opposite of the logarithm of the transmittance, expressed as follows: $A = -\log T$

It will be necessary to use the centrifuge Hermle z326K, centrifuge with possibility of cooling. Automatic pipettes of different microliter ranges from the Eppendorf Research Plus brand.

Tubes whose additive is dipotassium ethylenediaminetetraacetic acid (K2-EDTA) that will be centrifuged at 3500 revolutions per minute (rpm) for 10 minutes at 4 ° C will be used.

The plasma of the blood samples will be transferred to aliquots with a capacity of approximately 1.4 ml. The biological material to be transferred will be approximately 1 ml, regardless of the one obtained. The remaining plasma will be discarded to a biological container and destroyed according to the usual procedure and marked by the clinical trial with drugs.

The pertinence of this material resource could be justified by the following:

1. Coverage in the Clinical Trials Unit and Collaborating Researchers.

- 2. Acceptable capital, compared to other methods.
- 3. Objective method and sensitive to changes supported by Janish S et al (52).

2. Photoshop CC.

Application intended for the identification of the color of photographs. The program outputs the values in RGB and CMYK automatically.

3. Photographic camera

The photographs will be taken through the SONY® SLT-α58 camera with HD CMOS sensor and RGB filter with CE marking.

The design and validation of the scale are collected, in detail, in section 14.2.3.

| ORGANIZATION CHART OF CLINICAL FINDING ACCORDING TO VISITS | | |
|--|-----------------|---|
| FIRST PERIOD | WASH-OUT PERIOD | SECOND PERIOD |
| VAS/NUMERIC scale for pain assessment FITZPATRICK scale for skin assessment Hemolysis analysis 
 ▪ Baseline blood sample ▪ Afternoon blood sample ▪ Evening blood sample | X | VAS/NUMERIC scale for pain assessment Hemolysis analysis 
 ▪ Baseline blood sample ▪ Afternoon blood sample ▪ Evening blood sample |

Table 3. Organization chart of clinical findings according to visits. Own elaboration.

